9.2.5 Sample Size Determination

A sample size of at least 100 evaluable participants (i.e., 25 participants per treatment group) will provide >90% power to detect a 30% difference in LDL-C reduction at Day 56 (SD of 25%) for each of the obicetrapib groups compared to the placebo group at a 2-sided significance level of 0.05.

The sample size for this study was determined in order to provide sufficient power for the analyses of the primary efficacy endpoint described in Section 7. Therefore, assuming a dropout rate of approximately 7%, an estimated enrollment target of approximately 108 participants (i.e., 27 participants per treatment group) is planned for this study. This sample size will also contribute sufficient participant exposure and safety data.

Participants will be stratified according to their Screening Visit (Visit 1) LDL-C levels (≥100 or <100 mg/dL).

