Coronavirus Disease 2019 Contingency Measures

In cases of COVID-19 limitations, it is the Investigator's responsibility to assure the safety of participants. If investigators need to implement contingency measures, the investigators will communicate with the Sponsor and discuss the best practice with the sponsor. In the absence of a COVID-19 impact, it is expected that Investigators and participants follow the protocol requirements as set forth.

2.2.2 *Randomization and Blinding*

Participants who meet all eligibility criteria will be randomized into the study. Participants will be randomized in a 1:1:1:1 ratio to the 2.5 mg obicetrapib, 5 mg obicetrapib, 10 mg obicetrapib, or placebo treatment groups. At randomization, participants will be stratified according to their Screening Visit (Visit 1) LDL-C level (≥ 100 or < 100 mg/dL). An automated interactive response technology (IRT) system will be used to assign the participant to 1 of the 4 treatment groups, and visits will be registered in the IRT for Screening and Visits 1 through 5 as well as Early Termination, if applicable.

Participants, Investigators, the CRO, and the Sponsor will be blinded to all lipid results from Day 1 (Visit 2) for the first participant and continuing to database lock in order to protect blinding to treatment assignment.

2.2.3 *Study Drug*

The study drugs to be used in this study include the following:

- 2.5 mg obicetrapib tablet;
- 5 mg obicetrapib tablet;
- 10 mg obicetrapib tablet; and
- Matching placebo tablet.

The study drugs listed above will be packaged to provide doses of 2.5 mg, 5 mg, 10 mg obicetrapib, or placebo only. Placebo tablets will be visually identical. Participants will be randomized to receive 1 of the 3 doses of obicetrapib or placebo only. One tablet of study drug will be administered by the participant orally once daily from Day 1 (Visit 2) to Day 56 (Visit 5) at approximately the same time each morning.

2.2.4 *Sample Size Determination*

A sample size of at least 100 evaluable participants (i.e., 25 participants per treatment group) will provide $>90\%$ power to detect a 30% difference in LDL-C reduction at Day 56 (standard deviation (SD) of 25%) for each of the obicetrapib groups compared to the placebo group at a 2-sided significance level of 0.05.

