The sample size for this study was determined in order to provide sufficient power for the analyses of the primary efficacy endpoint described in Section 3.4. Therefore, assuming a dropout rate of approximately 7%, an estimated enrollment target of approximately 108 participants (i.e., 27 participants per treatment group) is planned for this study. This sample size will also contribute sufficient participant exposure and safety data.

Participants will be stratified according to their Screening Visit (Visit 1) LDL-C levels (≥ 100 or < 100 mg/dL).

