Counts and percentages of participants will be summarized by treatment for each type of data pattern. There will be 16 data patterns for four time points (Baseline, Day 14, Day 28 and Day 56) each having two possible outcomes (LDL-C data reported or missing).

Waterfall plot of percent change in LDL-C from Baseline to each scheduled visit will be created. Line plot of the mean (+/- 2 * SE) and the median (and IQR) percent change in LDL-C from Baseline to each scheduled visit will be created. Figures will be created for LDL-C values collected using two approaches described above.

The main analyses for the primary efficacy endpoint will be repeated for the ITT Population, the mITT On-Treatment Population, and PP Population.

Sensitivity Analyses

Three sensitivity analyses will be performed for the primary efficacy endpoint:

1. MMRM with imputation
2. Analysis covariance (ANCOVA)
3. ANCOVA using LDL-C by PUC

All sensitivity analyses will be conducted on the mITT Population.

Sensitivity Analysis 1

The first sensitivity analysis will be performed in two steps. In the first step, missing data will be assumed missing not at random (MNAR). Missing data at Days 14, 28 and 56 will be imputed using multiple imputation methodology in two steps. Initially, 25 data sets will be imputed for non-monotone missing values in the original dataset. In the second step the remaining monotone missing values in the 25 data sets will be imputed based on the observations in the Placebo group. Upon completion of the trial, if the percentage of cases with incomplete data is larger than initially anticipated then the number of imputations will be increased for the final analysis.

The variables for the imputation model will consist of LDL-C values from Baseline and Days 14, 28 and 56. For each imputation dataset, the percent change from Baseline to Day 56 will be analyzed using the MMRM model described for the primary analysis. The results from these 25 analyses will be combined using Rubin's method to construct the treatment estimates using the parameter estimates and associated standard errors. Similarly, the difference of the adjusted

treatment means (the three doses of obicetrapib therapy – Placebo) will be presented with the associated standard error and 95% confidence interval. Randomly chosen seed numbers will be selected for the analysis and will be retained.

Example SAS code to create a dataset for non-monotone missing values is shown below:

```
*****
```

Note:

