non-MONOTONE missing values

TREATMENT = 0 (Placebo), 1 (2.5 mg obicetrapib), 2 (5 mg obicetrapib), 3 (10 mg obicetrapib)

LDLC_BASE = LDL_C Baseline value

LDLC_Day14 = LDL_C value at Day 14

LDLC_Day28 = LDL_C value at Day 28

LDLC_Day56 = LDL_C value at Day 56

```
proc mi data=LDLC_Wide seed=20220101 out=LDLC_25MCMC n impute=25;
```

```
var TREATMENT LDLC_base LDLC_Day14 LDLC_Day28 LDLC_Day56;
```

```
mcmc impute=monotone chain=multiple;
```

```
run;
```

In the second step, the remaining monotone missing values will be imputed. Example SAS code to complete this step is shown below:

```
*****
```

Note:

MONOTONE missing values

TREATMENT = 0 (Placebo), 1 (2 mg obicetrapib), 2 (5 mg obicetrapib), 3 (10 mg obicetrapib)

LDLC_BASE = LDL_C Baseline value

LDLC_Day14 = LDL_C value at Day 14

LDLC_Day28 = LDL_C value at Day 28

LDLC_Day56 = LDL_C value at Day 56

```
proc mi data= LDLC_25MCMC seed=810456 out= LDLC_Mono n impute=1 simple;
```

```
by _Imputation;
```

```
class TREATMENT;
```

```
monotone method=reg;
```

```
mnar model (LDLC_Day14 LDLC_Day28 LDLC_Day56 / modelobs=(TREATMENT="0"));
```

```
var LDLC_base LDLC_Day14 LDLC_Day28 LDLC_Day56;
```

```
run;
```

For each imputation dataset, the percent change from Baseline to Day 14, Day 28 and Day 56 will be analyzed using similar MMRM approach. Then the parameter estimates will be combined using Rubin's method. Example SAS code to combine the parameter estimates is shown below:

```
*****
```

Note:

MIANALYZE to combine imputations

```
*****
```

```
proc mianalyze parms(classvar=full)=mixLSM;
```

```
class TREATMENT;
```

```
modeleffects TREATMENT;
ods output parameterestimates=mi_LSM;
run;
proc mianalyze parms(classvar=full)=mixDIFF;
  class TREATMENT;
  modeleffects TREATMENT;
  ods output parameterestimates=minus_mi_DIFF;
run;
*****
```

Sensitivity Analysis 2

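### Sensitivity Analysis 1 enters treatment arm as a continuous variable in its first imputation step, and does not say how much drug effect its placebo-based second step carries past dropout

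*SAP*

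**What the plan says.** SAP 3.4.1 analyses the primary endpoint with an MMRM that assumes MAR and imputes nothing. Sensitivity Analyses 2 and 3 are ANCOVAs, also without imputation. SA1 is the only multiple-imputation analysis of the endpoint, and it works in two stages.

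- **Step 1 (intermittent gaps).** PROC MI with MCMC completes the non-monotone gaps. Its variable list is "var TREATMENT LDLC_base LDLC_Day14 LDLC_Day28 LDLC_Day56", with no CLASS statement. TREATMENT is a code from 0 (placebo) to 3 (10 mg). The introductory text describes missing data as MNAR, but the MCMC call has no MNAR statement.
- **Step 2 (dropout).** The remaining "monotone missing values in the 25 data sets will be imputed based on the observations in the Placebo group". The code uses monotone regression fitted to placebo observations only, with the list "var LDLC_base LDLC_Day14 LDLC_Day28 LDLC_Day56". Each missing visit is therefore predicted from all earlier visits. The text also names Baseline and Days 14, 28 and 56 as the imputation variables.

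Neither document says what SA1 assumes about the drug effect once a participant stops. No jump-to-reference, delta-adjusted or tipping-point analysis is planned.

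**The concern.** **Step 1.** A nominal arm in a multivariate-normal MCMC becomes a numeric predictor. The model then forces equal LDL-C steps from placebo to 2.5 mg, 5 mg and 10 mg. A dose-response that flattens does not follow that line. The PROC MIXED and PROC GLM models and step 2 itself all declare TREATMENT as a class variable, so step 1 stands alone.

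**Step 2.** The regression coefficients come from placebo, but they are applied to the dropout's own values. An obicetrapib participant with low LDL-C at Day 28 is imputed as a placebo participant who happened to run low. Part of that low value persists at Day 56, which is a copy-reference type of assumption. Because SA1 is the only check on informative dropout, a report could present it as evidence of robustness to complete loss of effect, which it does not examine.

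**Working it through.** **1. The plan's own figures reproduce.** Inputs are from Protocol 9.2.5 and SAP 2.2.4: "A sample size of at least 100 evaluable participants (i.e., 25 participants per treatment group"), difference 30, SD 25, two-sided 0.05.
- z = 30 / (25 × √(2/25)) = 4.24, so power = Φ(4.24 − 1.96) ≈ 0.989, above the stated 90%.
- At 7% dropout, 25 / 0.93 = 26.9, so 27 per arm and 4 × 27 = 108, as stated. That is about two dropouts per arm.

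**2. Step 1: effect of the numeric arm code.** The documents give no inputs for this. Assumptions:
- Day 56 changes of 0, −30, −38 and −45% for codes 0 to 3;
- effect at Days 14, 28 and 56 in the ratio 38:42:45, so s = (0.844, 0.933, 1), with 0 at Baseline;
- mean LDL-C 100 mg/dL, SD 25 mg/dL, exchangeable visit correlation r of 0.6 to 0.9.

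The least-squares line through the four arm values has slope −14.3 and intercept −6.8. Fitted values are −6.8, −21.1, −35.4 and −49.7. The misfit e (fitted minus assumed) is −6.8, +8.9, +2.6 and −4.7 points.

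Conditioning on the participant's other visits shrinks this. The remaining bias is e × (s_t − b·s_o) / (1 + q·h). Here t is the missing visit and o the observed ones. The weights b are each r/(1 + 2r), W_oo is the within-arm covariance of the observed visits, and h = s_o′ W_oo⁻¹ s_o. The mean squared misfit is q = (6.8² + 8.9² + 2.6² + 4.7²)/4 = 38.6.
- Largest (r = 0.6, Day 28 missing, 2.5 mg): b = 0.273; 0.933 − 0.273 × 1.844 = 0.430; q·h = 0.121; bias = 8.9 × 0.430/1.121 = 3.4 mg/dL.
- Smallest (r = 0.9, Day 14 missing, 5 mg): b = 0.321; 0.844 − 0.321 × 1.933 = 0.223; q·h = 0.413; bias = 2.6 × 0.223/1.413 = 0.4 mg/dL.

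Day 56 is last in the variable list, and this MCMC call fills only what is needed to make the pattern monotone. Step 1 therefore never imputes Day 56 itself. The bias can reach Day 56 only indirectly, through the MMRM covariance or as a step 2 predictor.

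**3. Step 2: share of the effect carried to Day 56.** This is the placebo coefficients for Day 56 applied to the dropout's treatment shift at observed visits, with no shift at Baseline. The assumed profile is −38, −42 and −45% at Days 14, 28 and 56.
- Exchangeable correlation r: r/(1+r) × 38/45 if Day 14 is the last value; r/(1+2r) × (38+42)/45 if Day 28 is.
- Autoregressive, r per 28 days: r^1.5 × 38/45 and r × 42/45.

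| r | Exch., last Day 14 | Exch., last Day 28 | AR, last Day 14 | AR, last Day 28 |
|---|---|---|---|---|
| 0.3 | 20% | 33% | 14% | 28% |
| 0.6 | 32% | 48% | 39% | 56% |
| 0.9 | 40% | 57% | 72% | 84% |

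With no post-baseline value the share is 0. Simulating the sequential placebo regressions with a constant effect and exchangeable r = 0.5 gave 0.33 and 0.50. These match r/(1+r) and 2r/(1+2r), the same formulas with a constant effect.

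**4. Consequence at planned dropout.** The expected difference is 30 × [1 − 0.07 × (1 − c)] for carried share c, with every dropout missing Day 56. Power is approximate, at 27 per arm, and ignores imputation variance.

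| Assumption | Difference | Power |
|---|---|---|
| Full loss of effect, c = 0 | 27.9 | 98.4% |
| c = 1/3 | 28.6 | 98.8% |
| c = 2/3 | 29.3 | 99.1% |
| MAR, c = 1 | 30.0 | 99.3% |

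SA1 is thus milder than full loss by 0.07 × 30 × c, or 0.7 to 1.4 points. On a 45-point effect the same shares give 0.07 × 45 × c = 1.05 to 2.1. Over the whole 14 to 84% range, the 30-point figure is 0.3 to 1.8.

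**The case against.** A reader might infer that SA1 is weaker than the SAP describes. The documents do not support that. The text lists the earlier LDL-C visits as imputation variables, the step 2 code uses them, and nowhere is full loss of effect promised. Placebo-based imputation conditional on a participant's own history is a recognised MNAR scenario. The primary analysis follows a while-on-treatment strategy, and no LDL-C offset rate is given, so immediate return to placebo is not shown to be the right benchmark. All of this stands.

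A reader might also quote one figure for the carried share, such as a third to two thirds. That is not a document figure. It depends on visit correlations and an effect profile that the plan does not state, and it is zero for anyone without a post-baseline value.

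On size, about two dropouts per arm cannot move the result much. The figures are upper bounds for dropouts, because early termination includes a lipid profile and SAP 3.1.2 assigns values from Day 43 to Day 70 to Week 8. Values removed under the while-on-treatment rules could add missingness in the other direction.

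On step 1, the code is labelled as an example, and SAP section 6 defers detailed specifications to a separate document. That is fair, but the example is the only specification in view, and it contradicts the SAP's other models.

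**Conclusion.** Two limited points hold.

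1. Step 1 misspecifies the arm. The error is about 0.4 to 3.4 mg/dL per imputed Day 14 or Day 28 value under the assumed dose-response, SD and exchangeable correlations of 0.6 to 0.9. It has almost no effect on Day 56. The MNAR description does not fit this step, because ordinary MCMC assumes MAR.
2. Step 2 is coherent with its text, but its post-discontinuation assumption is unstated. It carries none of the effect for participants with no post-baseline LDL-C. For the others it carries about 14 to 84% over assumed correlations of 0.3 to 0.9. It should not be reported as a test of full loss of effect.

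At 7% dropout and the planning effect, the distance from full loss is about 0.7 to 1.4 points in 30 for a carry of one to two thirds. Power stays above 98% either way, so the trial's conclusion would not turn on it. The gap grows with missingness: at 15% dropout, full loss gives 30 × 0.85 = 25.5, against 27.0 to 28.5 for the same shares.

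**What to change.** - **Step 1 code:** run PROC MI BY TREATMENT, with TREATMENT dropped from the variable list and the output re-sorted by imputation number before step 2. Alternatively, replace TREATMENT by three 0/1 arm indicators, which keeps a common covariance with about 27 participants per arm.
- **Step 1 text:** say that intermittent gaps are imputed under MAR and that only the monotone gaps are imputed under MNAR.
- **Step 2 text:** add a sentence saying that monotone gaps are imputed from placebo regressions on the participant's own earlier LDL-C, so part of any on-treatment effect is carried forward. Say also that SA1 does not represent full loss of effect.
- **Optional:** beside SA1, add a standard jump-to-reference analysis or a delta/tipping-point analysis. A jump-to-reference analysis should keep each participant's own residuals and be limited to those who stopped study drug. A regression of Day 56 on Baseline alone would discard those residuals and, unless restricted, would fill every missing Day 56.

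The corrections cost a few lines of text and code before database lock. The optional analysis costs one extra table, probably with a slightly less favourable estimate.

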3.4.2 Secondary Efficacy Endpoints

Similar MMRM models as described for the primary efficacy analyses will be used to analyze the secondary efficacy endpoints based on the mITT Population. No adjustment will be made for multiplicity in testing the secondary efficacy endpoints. Nominal p-values will be provided when applicable.

Values, changes from Baseline, and percent change from Baseline of each lipid profile will be summarized using descriptive statistics at scheduled visits and Baseline by treatment group. The following endpoints will be examined:

- Percent change from Day 1 to Day 56 in ApoB for each obicetrapib group compared to the placebo group;
- Percent change from Day 1 to Day 56 in non-HDL-C for each obicetrapib group compared to the placebo group; and
- Percent change from Day 1 to Day 56 in HDL-C for each obicetrapib group compared to the placebo group.

Waterfall plot of percent change in ApoB from Baseline to each scheduled visit will be created.

3.4.3 Other Efficacy Endpoints

The percent change from Day 1 to Day 56 in Apolipoprotein E (ApoE), Triglycerides, and Very low-density lipoprotein cholesterol will be examined through similar MMRM models as described for the primary efficacy analyses based on the mITT Population. Values, changes from Baseline, and percent change from Baseline of each lipid profile will be summarized using descriptive statistics at scheduled visits and Baseline by treatment group.

3.4.4 Subgroups

Not applicable.

3.5 Pharmacokinetic Assessment

Plasma obicetrapib concentrations will be summarized with descriptive statistics based on the PK Population. Exploration of any relationships with obicetrapib exposure will be performed, as appropriate.

On Day 1, a PK sample will be collected pre-dose. The subsequent post-dose PK samples should be collected once at approximately the same time at each visit.

3.6 Pharmacodynamic Assessment

Not applicable.

3.7 Safety Assessment

The Safety Population will be the primary population for the safety analyses. All safety endpoints will be summarized descriptively. No statistical inference will be applied to the safety endpoints.

3.7.1 Adverse Events (AEs)

AEs will be categorized by primary system organ class and preferred term as coded using the MedDRA (with the version specified in Data Management Plan) category designations.

Treatment-emergent adverse events (TEAEs) are defined as AEs that start after the first dose of study drug.

Adverse events of special interest will be flagged in CRF.

An overview of AEs will be provided including counts and percentages of participants (and event counts) by treatment and in total with the following:

- Any TEAEs overall and by maximum severity
- Any study drug related TEAEs overall and by maximum severity
- Any TEAEs of special interest
- Any treatment-emergent serious AEs (TESAEs)
- Any study drug related TESAEs
- Any TEAEs leading to discontinuation of study drug
- Any AEs leading to death

Counts and percentages of participants (and event counts) will also be presented by system organ class and preferred term for each of the categories in the overview.

Listings will be presented specifically for TEAEs, TESAEs, TEAEs leading to discontinuation of study drug, and TEAEs of special interest.

3.7.2 Clinical Laboratory Tests

Blood and urine samples for clinical laboratory tests will be collected at timepoints indicated in Appendix A (Schedule of Procedures) of the study protocol and processed by a central laboratory. See Appendix B for a complete list of analytes.

Blood samples for chemistry and hematology must be obtained under fasting conditions (i.e., after the participant has fasted for approximately 8 hours). For the purposes of this study, fasting will be defined as nothing by mouth except water and any essential medications. If a participant is not fasting, the Investigator should reschedule the visit as soon as possible. Estimated glomerular filtration rate will be calculated using the Chronic Kidney Disease Epidemiology Collaboration equation. At the Screening Visit only, the chemistry panel will include HbA1c.

A urine pregnancy test will be performed for women of childbearing potential at the Screening Visit (Visit 1) prior to their participation in the study and at the Safety Follow-Up Visit (Visit 6), and the Early Termination Visit, if appropriate.

An FSH test will be performed at the Screening Visit prior to participation in the study in women <55 years of age for whom it has been ≥ 1 year since their last menstrual period to confirm a postmenopausal state.

For each laboratory test, values, changes from Baseline, percent change from Baseline will be presented at each scheduled visit and Baseline by treatment and in total. According to the availability of laboratory data, additional shift tables will be presented to describe the change in laboratory parameter values at post-Baseline visits using normal range categories (low, normal, and high).

3.7.3 Vital Signs

Vital signs will include body temperature, heart rate, and triplicate blood pressure (systolic and diastolic) measurements and measured at all scheduled timepoints. Participants should be in the supine position after at least 10 minutes rest prior to the vital sign measurements.

Weight and height will be measured at the Screening Visit and will be used to calculate body mass index as following:

$$BMI(kg/m^2) = weight(kg)/(height(m))^2$$

Measurement of weight should be performed with the participant dressed in indoor clothing, with shoes removed, and bladder empty.

Values and changes from Baseline will be summarized with descriptive statistics at each visit by treatment.

3.7.4 Electrocardiograms

A single, standard 12-lead ECG will be performed by the Investigator or trained site personnel at the Screening Visit and read locally. Summary statistics will be provided for the overall interpretation by treatment and in total. A separate data listing by participant will be provided for ECG data.

3.7.5 Physical Examinations

Physical examinations will be performed at Screening Visit and Visit 5. Data collected related to physical examinations will be listed.

3.7.6 Events of Special Interest

Liver-associated enzymes and total bilirubin will be summarized by the value and change from Baseline in the value, by treatment group and visit. In addition, the number and percent of participants with abnormal values for ALT, AST, and total bilirubin will be summarized. These summaries of participants with abnormal values will be performed overall; by normal Baseline; and by abnormal Baseline for ALT, AST, and total bilirubin individually. Hy's Law criteria ($>3 \times$ ULN for either ALT or AST, with accompanying total bilirubin $>2 \times$ ULN) will also be applied to the data. Any potential Hy's Law cases will be listed separately.

Muscle-related abnormalities will be summarized by treatment group. CK levels will be summarized by the value and change from Baseline in value, by treatment group and visit. In addition, the number and percent of participants with abnormal CK values will be summarized. These summaries of participants with abnormal CK values will be performed overall, by normal Baseline CK, and by abnormal Baseline CK.

Cases of NODM will be recorded and summarized using the appropriate system organ class. These events will be summarized by severity and relationship to study drug for each treatment group. Fasting plasma glucose and HbA1c will be monitored as specified in Appendix A (Schedule of Procedures) of the study protocol.

Baseline eGFR will be summarized by treatment group for actual value and for Baseline eGFR categories. Shift tables of eGFR category from Baseline to End of Treatment (EOT) will be provided by treatment group. Shift tables of urine albumin-creatinine ratio and urine protein creatinine ratio from Baseline to EOT will be provided by treatment group. Values of CK from Baseline to EOT will be summarized by treatment group and by Baseline eGFR category. Muscle related abnormalities will be summarized by treatment group and by Baseline eGFR category.

Cases of macular degeneration will be recorded and summarized using the appropriate system organ class. These events will be summarized by severity and relationship to study drug for each treatment group.

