Clinically significant abnormal laboratory or other examination findings (e.g., ECG) that are detected during the study or are present at the Screening Visit (Visit 1) and significantly worsen during the study should be reported as AEs, as described below. The Investigator will exercise his or her medical and scientific judgment in deciding whether an abnormal laboratory finding, or other abnormal assessment is clinically significant. Clinically significant abnormal laboratory values occurring during the study will be followed until repeat tests return to normal, stabilize, or are no longer clinically significant. Abnormal test results that are determined to be an error should not be reported as an AE. Laboratory abnormalities or other abnormal clinical findings (e.g., ECG abnormalities) should be reported as an AE if any of the following are applicable:

- If an intervention is required as a result of the abnormality;
- If action taken with the study drug is required as a result of the abnormality; or
- Based on the clinical judgment of the Investigator.

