8.1.4 Events of Special Interest

Events of special interest (ESIs) will be monitored over time, regardless of whether these events were reported as AEs. Any events that qualify as an AE or SAE will be reported accordingly (see Sections 8.1, 8.2, and 8.3).

ESIs will include hepatic abnormalities, muscle-related abnormalities, new-onset diabetes mellitus (NODM) and/or hyperglycemia, renal abnormalities, and ophthalmic events (i.e., macular degeneration), described as follows:

- AST or ALT >3 × ULN;
- Bilirubin >2 × ULN;
- CK >5 × ULN;
- NODM or worsening of glycemic control;

Note: NODM is defined by 1 or more of the following criteria, based upon information from AE, medication, and laboratory data:

- o AE indicating new type 1 or type 2 diabetes;
- o Initiation of anti-diabetes medication with confirmation of the diagnosis of diabetes;
- HbA1c \geq 6.5% (48 mmol/mol); and/or
- o Two consecutive values of fasting plasma glucose that are ≥ 126 mg/dL (7.0 mmol/L).

Note: Worsening of glycemic control will be defined as an HbA1c increase from Baseline >0.5% and/or a new concomitant medication or increase in current antidiabetic therapy in a participant with a Baseline HbA1c $\ge 6.5\%$.

- Both eGFR <30 mL/min/1.73 m² AND a >25% decrease in eGFR from Baseline, calculated using the Chronic Kidney Disease Epidemiology Collaboration equation; and
- Macular degeneration.

These ESIs will be monitored through review of the AE and laboratory databases.

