9.2.2.1 Analysis of events of special interest

Liver-associated enzymes and total bilirubin will be summarized by the value and change from Baseline in the value, by treatment group and visit. In addition, the number and percent of participants with abnormal values for ALT, AST, and total bilirubin will be summarized. These summaries of participants with abnormal values will be performed overall; by normal Baseline; and by abnormal Baseline for ALT, AST, and total bilirubin individually. Hy's Law criteria ($>3 \times$ ULN for either ALT or AST, with accompanying total bilirubin $>2 \times$ ULN) will also be applied to the data. Any potential Hy's Law cases will be listed separately.

Muscle-related abnormalities will be summarized by treatment group. CK levels will be summarized by the value and change from Baseline in value, by treatment group and visit. In addition, the number and percent of participants with abnormal CK values will be summarized. These summaries of participants with abnormal CK values will be performed overall, by normal Baseline CK, and by abnormal Baseline CK.

Cases of NODM will be recorded and summarized using the appropriate system organ class. These events will be summarized by severity and relationship to study drug for each treatment group. Fasting plasma glucose and HbA1c will be monitored as specified in Appendix A.

Baseline eGFR will be summarized by treatment group for actual value and for Baseline eGFR categories. Shift tables of eGFR category from Baseline to End of Treatment (EOT) will be provided by treatment group. Shift tables of urine albumin-creatinine ratio and urine protein-creatinine ratio from Baseline to EOT will be provided by treatment group. Values of CK

from Baseline to EOT will be summarized by treatment group and by Baseline eGFR category. Muscle-related abnormalities will be summarized by treatment group and by Baseline eGFR category.

Cases of macular degeneration will be recorded and summarized using the appropriate system organ class. These events will be summarized by severity and relationship to study drug for each treatment group.

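### The planned summary of glycaemic events of special interest does not count cases that lack an AE record and has no entry for worsening of glycaemic control

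*SAP*

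**What the plan says.** Protocol 8.1.4 states that events of special interest "will be monitored over time, regardless of whether these events were reported as AEs". The glycaemic one is "NODM or worsening of glycemic control". Its note on new-onset disease reads "NODM is defined by 1 or more of the following criteria, based upon information from AE, medication, and laboratory data". There are four criteria: an AE of new diabetes, starting anti-diabetes medication with a confirmed diagnosis, HbA1c of at least 6.5%, or two consecutive fasting plasma glucose values of at least 126 mg/dL. Worsening has its own definition: an HbA1c rise of more than 0.5%, and/or new or increased therapy, in a participant with Baseline HbA1c of at least 6.5%.

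The analysis sections are shorter. SAP 3.7.6 says "Cases of NODM will be recorded and summarized using the appropriate system organ class", and protocol 9.2.2.1 has the same sentence and adds "These events will be summarized by severity and relationship to study drug for each treatment group". Neither mentions worsening. SAP 3.7.1 says "Adverse events of special interest will be flagged in CRF" and tabulates and lists treatment-emergent AEs of special interest.

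**The concern.** The definition draws on three data sources and two kinds of event. The dedicated summary names one kind of event and describes it with attributes that come from one source. Followed as written, the table can show fewer glycaemic events than the protocol's own definition yields, and the shortfall depends on which glucose results investigators choose to report. Safety and tolerability are a stated secondary objective. A low or empty NODM row could be read as absence of a glycaemic signal when it partly reflects AE reporting. Participants with Screening HbA1c below 10% may enroll, so people with existing diabetes can be in the trial. For those with Baseline HbA1c of at least 6.5%, worsening is the event that applies, and it has no dedicated summary.

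**Working it through.** The plan states no figure for this point, so the check is a comparison of texts.

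**Step 1: which records carry the summary attributes.** Severity and relationship are investigator assessments of each AE (protocol 8.1.3). System organ class comes from coding AEs (protocol 9.2.2, SAP 3.7.1). A glucose result or a medication record has no severity or relationship grade and no AE system organ class.

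**Step 2: when a glucose result becomes an AE.** Protocol 8.1 requires an AE if the abnormality needs an intervention, if it needs action on study drug, or "Based on the clinical judgment of the Investigator". Two untreated values of at least 126 mg/dL that lead to no action on study drug are reported only if the investigator so judges.

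**Step 3: trace each case type to an output.**

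| Case type | Protocol 9.2.2.1 / SAP 3.7.6 | Other planned output |
|---|---|---|
| NODM reported as an AE | Counted | SAP 3.7.1 AE tables; special-interest table and listing if flagged |
| NODM by starting medication | Counted if also an AE, which protocol 8.1 makes likely | Concomitant medication table (SAP 3.3.6) |
| NODM by two glucose values only | No count | Glucose values and range shifts by visit (SAP 3.7.2) |
| Worsening reported as an AE | No summary | SAP 3.7.1 AE tables; special-interest table and listing if flagged |
| Worsening by therapy change, no AE | No summary | Concomitant medication table |
| NODM or worsening by HbA1c | Not assessable from scheduled post-Baseline data | None |

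The glucose summaries do not replace a case count. They describe values and low, normal or high categories visit by visit. The criterion links two consecutive values within one participant at a fixed threshold.

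The last row follows from the schedule. Protocol 8.7, Appendix A and Appendix B take HbA1c at Screening only, although protocol 9.2.2.1 and SAP 3.7.6 say it will be monitored as Appendix A specifies.

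**Step 4: compare with the other events in the same section.** SAP 3.7.6 gives participant counts from laboratory data for ALT, AST, bilirubin and CK, and applies Hy's Law criteria to the data. The glycaemic event, also defined partly on laboratory data, gets no such count. SAP section 5 lists no change to the definition.

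**Step 5: size, for illustration only.** One participant in an arm of 27 is 1/27 = 3.7 percentage points. Let p be the assumed rate under 8.1.4 and c the assumed fraction also reported as AEs. The expected displayed count is 27pc, and the chance that an arm shows zero is (1 − pc)^27.

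- p = 10%, c = 100%: 2.7 expected; 0.900^27 = 0.058
- p = 10%, c = 75%: 2.0 expected; 0.925^27 = 0.122
- p = 10%, c = 50%: 1.4 expected; 0.950^27 = 0.250
- p = 10%, c = 25%: 0.7 expected; 0.975^27 = 0.505
- p = 2%, c = 100%: 0.5 expected; 0.980^27 = 0.580

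The last line shows that at a low true rate an empty row is likely even with full capture. If 20–40% of 108 participants had Baseline HbA1c of at least 6.5%, worsening would be the applicable event for 0.20 × 108 = 22 to 0.40 × 108 = 43 of them. That is a number at risk, not a number of missed events.

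**The case against.** A reader might infer that worsening vanishes from the safety tables. It does not. Protocol 8.1 requires a pre-existing condition that changes in severity to be reported as an AE, and SAP 3.7.1 tabulates all treatment-emergent AEs and those of special interest, without limiting either to NODM. Glucose is summarised under SAP 3.7.2, and SAP section 6 promises listings of all data.

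A reader might also infer that the plan restricts NODM to AE records or defines it a second time. Neither is stated. The AE restriction is an inference from the attributes used, and the only definition is in protocol 8.1.4. The separate programming specifications, which are not public, could contain a derivation.

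The medication route is largely covered as well, because an abnormality that needs an intervention is to be reported as an AE. Finally, safety is summarised descriptively without inference, so no formal test depends on this table.

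All of this stands and narrows the point. It leaves two gaps: cases met without an AE record, mainly by glucose alone, have no planned count, and worsening has no dedicated summary. Listings hold the raw data, but a reader would have to derive the cases by hand.

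**Conclusion.** The point holds in a limited form. Protocol 9.2.2.1 and SAP 3.7.6 do not carry the protocol 8.1.4 definition into a count. They omit worsening and give no rule for deriving cases that were not reported as AEs. This can lower the reported number of glycaemic events of special interest; it does not affect the primary endpoint.

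The size cannot be fixed from the documents. The event rates of 2% and 10%, the AE capture fractions of 25–75% and the diabetes prevalence of 20–40% are illustrative assumptions, not forecasts. The firm figure is that one uncounted participant in a planned arm of 27 is 3.7 percentage points. The change is worth making before database lock because it alters the reported counts and uses data already collected.

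**What to change.** In SAP 3.7.6 and protocol 9.2.2.1:

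- Add a derived participant-level count by arm of those meeting any 8.1.4 NODM criterion after first dose. Restrict it to participants without diabetes at Baseline, judged by medical history, antidiabetic medication or Screening HbA1c of at least 6.5%. Without this restriction, existing diabetes would be counted as new-onset.
- Split the count by source: AE, medication, fasting glucose, and HbA1c where available.
- Add a separate row for 8.1.4 worsening among participants with Baseline HbA1c of at least 6.5%.
- Show the denominator for each row. Participants with known or treated diabetes but HbA1c below 6.5% fall in neither row, and the table should show how many there are.
- Keep severity and relationship only for cases that are AEs.

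In SAP 3.7.1, label the special-interest treatment-emergent AEs as the AE-reported subset of the 8.1.4 events.

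The HbA1c criteria and the Screening-only schedule contradict each other and must be reconciled. Until then, the table should state that the HbA1c criteria cannot be assessed from scheduled post-Baseline data.

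The cost is a few lines of text and derived flags. Fasting chemistry and concomitant medication are already collected at every visit, so the glucose and medication criteria need no new samples. Displayed counts may rise, and some cases will have no severity or causality grade.
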